8.1. Statistical Design, Method and Analysis Regulation

8.1.1 Statistical Design (Hypothesis Inspection)

The current trial adopts perspective, multiple centered, randomized control design and the comparing type is non-inferiority trial. Through the comparison with the similar products already marketed, it has been proved that the trial instrument can meet the clinical application needs in the same way, and for the primary evaluation index, it is setup as the occlusion successful rate 6 months after implanting in evaluation during operation, and the corresponding statistical hypothesis inspection is :

$$H_0 : p_T - p_C \leq -\Delta$$

$$H_1 : p_T - p_C > -\Delta$$

In the equation p_T , it corresponds to occlusion successful rate 6 months after implanting in the trial group, and p_C represents the occlusion successful level 6 month after implanting in the control group, Δ represents non-inferiority limit value (here it is positive value).

8.1.2 Statistical Analysis Method

- (1) Description analysis: The counting data were described with frequency number and composing rate; and the measurement data applied mean value, standard deviation,

maximum value, minimum value, as well as the median value, 25 and 75 percentiles.

- (2) Baseline demographic statistical analysis: On the basis of descriptive analysis, between the counting data groups, it applies continuous calibration χ^2 inspection, when the unit block theoretical frequency number over 25% is lower than 5, it applies the Fisher's Exact Test; for normal distribution, the comparison between different counting data groups, it applies grouping t Test; for abnormal distribution, it applies Wilcoxon Rank and Wilcoxon Rank Sum Inspection for comparison between groups.
- (3) Efficacy Analysis: For occlusion successful rate 6 months after implanting as the primary efficacy indices, it applies the adjustment of central effect with CMH Chi-square test as the method to compare between different groups, apart from the assessment for the successful rate between trial and control groups, it should also be assessed for the difference value between successful rate in different groups as well as 95% confidence interval. For other efficacy indices, the comparison method between groups is similar as the baseline analysis. For within group counting data comparison with normal distribution, it applies matched t Test; for within group counting data comparison with abnormal distribution, it applies Wilcoxon Sign Rank Test.
- (4) Safety Evaluation: Describe the case number of normal before treatment and abnormal after treatment and their percentage respectively according to the test group and control group. Described the adverse events with the case number of adverse events and their occurrence, and carried out continuous calibration χ^2 test or Fisher precision probability method test. At the same time, it shall be described in details of the embodiment for all adverse events, their degrees and relevance with the research products.
- (5) For primary efficacy indices, the statistical analysis shall be carried out under the significance level with 0.025 on single side (which correspond to 95% confidence interval on one side confidence limit), for other indices, all the statistical analysis

shall be carried out under significance level with 0.05 on both sides (excluding specifically annotated otherwise).It applies SAS[®] 9.4 statistical software for statistical analysis.

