8.1.3. Statistical Analysis Regulation

Relevant links involved in the statistical analysis shall all comply with the prescription in ICH E9, as well as the relevant requirements in the “Biological Statistical Guiding Principles in Clinical Trial” released by CFDA. At the same time, all the analysis procedures shall all be strictly implemented according to the Standard Operation Procedures (SOP) released by Medical Statistical Department in National Cardiovascular Diseases Center.

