8.2 Sample Volume Calculation

8.2.1 Total Sample Volume

It is expected of 108 cases of patients included in the trial, randomized into the trial group or control group with the ratio of 1:1, with 54 cases in each group. The calculation of sample volume is based on the primary evaluation indices, namely the 6 months occlusion successful rate after implanting.

In combination of the current clinical evidence and experience assessment by the clinical experts, it is assumed that the 6 months occlusion successful rate is about 98% after implanting in patients of the control group, it is expected the trial products in the trial group in application can also reach the same successful rate level, it is determined by clinician and sponsor after joint discussion that the non-inferiority limit value is set as 8%, when the significance level for statistical test takes 2.5% on single side, with test power of 80%, taking into account of the maximum incidence of 10% falling off rate and randomized block length in the research, according to statistical principles, it is calculated that, for each group, it is necessary for 54 cases of patients inclusion, total case number in both groups are 108 cases.

The corresponding sample volume calculation equation is:

$$n = \frac{\left[\mu_{1-\alpha} \sqrt{2\bar{p}(1-\bar{p})} + \mu_{1-\beta} \sqrt{p_T(1-p_T) + p_C(1-p_C)} \right]^2}{(\Delta - (p_T - p_C))^2}$$

In the equation p_T correspond to the 6 months occlusion successful rate after implanting in trial group, and p_C represents 6 months occlusion successful rate after implanting in control group; $\bar{p} = (p_T + p_C)/2$ is average successful rate between both groups; Δ corresponds to non-inferiority limit value; μ represents the percentile of standard normal distribution, α corresponds to Type I error level for statistical test, which is 0.025 here, while β corresponds to Type II error level for test, when calculated, it takes 0.2 (corresponding to 80% of test power).

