8.3 Significance level and Test Power for Clinical Trial

In the current trial, the significance level for the statistical test shall take 5%(on both sides)(unless specified otherwise), and the test power take 80%.

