8.5 Eligible/Ineligible Criteria of Clinical Trial Results

From statistical angle, it is judged of the eligibility and ineligibility of the trial results, correspond to the validation for initial hypothesis inspection. For the current research, the primary evaluation index is the 6 months occlusion successful rate after implanting, and the comparison type of the trial is non-inferiority inspection, which is planned to be proved through trial result. Compare the trial group and control group product, they both have the same treatment efficacy.

In conclusion, the judgment of trial results shall be based on the difference between the occlusion successful rates in the trial group and the control group, if the results demonstrate: The occlusion successful rate in trial group subtracting that in control group in the lower limit of 95% confidence interval is greater than -8% (the non-inferiority limit value setup in advance), it can be explained as non-inferiority conclusion is established. Otherwise, the non-inferiority conclusion can not be reached.

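### The method for the 95% limit that decides non-inferiority is not named, and none of four common unstratified limits gives both the stated 2.5% error and the stated 80% power

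*Combined protocol and SAP*

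**What the plan says.** All references are to the combined protocol and SAP.

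- **8.1.1** states that "the comparing type is non-inferiority trial" and sets H0: pT - pC <= -Δ against H1: pT - pC > -Δ.
- **8.5** makes one number decisive. Non-inferiority is concluded if, for test minus control, the "lower limit of 95% confidence interval is greater than -8" per cent.
- **8.1.2(3)** says of the primary endpoint that "it applies the adjustment of central effect with CMH Chi-square test as the method to compare between different groups". It adds that "it should also be assessed for the difference value between successful rate in different groups as well as 95% confidence interval". No interval method, variance or weighting is given.
- **8.1.2(5)** sets one-sided 0.025 for the primary endpoint, "which correspond to 95% confidence interval on one side confidence limit".
- **8.2.1** assumes 98% success in both arms and a margin of 8 points, "when the significance level for statistical test takes 2.5% on single side, with test power of 80" per cent. With up to 10% loss it arrives at 54 per arm. **8.3** repeats the 80%.
- **8.9** runs the primary analysis on both FAS and PPS, and fills missing primary outcomes in the FAS by WCCF.
- **8.1.3, 8.7 and 8.8** leave detail to an institutional SOP and to an analysis prospectus that must be final before database lock. Neither is among the documents.

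**The concern.** The decision rule is sound in form: a two-sided 95% interval for the difference, read at its lower end, is a one-sided 2.5% test of the null in 8.1.1. The rule is incomplete, because the number it compares with -8% is not defined. The CMH test does not fill the gap. It tests pT = pC, so its p-value says nothing directly about pT - pC <= -8%. The equation in 8.2.1 sizes the trial and does not define an interval.

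In many trials the common limits nearly agree and this would be a detail. Here success is expected at 98%, so 108 x 0.02 = 2.16 failures are expected in the whole trial. With so few events the limits separate widely, and they do so on the most likely results. A reader cannot tell whether the planned trial has roughly the stated power with an inflated error, or a controlled error with roughly half the stated chance of failure-free approval of the hypothesis that 80% power implies. The registration conclusion can turn on that choice.

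**Working it through.** **1. The plan's own figure.** Inputs from 8.2.1: pT = pC = 0.98, Δ = 0.08, one-sided α = 0.025, power 80%, loss 10%. Since pT = pC, both square roots in the formula equal √(2 x 0.98 x 0.02) = √0.0392, so

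n = (1.960 + 0.842)² x 0.0392 / 0.08² = 48.07; 48.07 / 0.9 = 53.4, hence 54 per arm.

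The stated size reproduces. It rests on a normal approximation, which need not describe the behaviour of any particular limit at 98%.

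**2. Limits on likely results (54 per arm, lower limit in %).** Wald: d - 1.96 √[p1(1-p1)/54 + p2(1-p2)/54]. Continuity-corrected (CC) Wald subtracts a further 0.5(1/54 + 1/54) = 1.85 points. MN inverts the score test with the variance restricted to the null difference.

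For one failure in each arm: d = 0, SE = √[2 x (53/54)(1/54)/54] = 2.595%, so Wald = -1.96 x 2.595 = -5.1 and CC Wald = -5.1 - 1.85 = -6.9. MN gives -8.2.

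| Failures, test v control | Probability at 98% v 98% | Wald | CC Wald | MN |
|---|---|---|---|---|
| 1 v 0 | 12.4% | -5.4 | -7.3 | -9.8 |
| 1 v 1 | 13.7% | -5.1 | -6.9 | -8.2 |
| 2 v 2 | 4.0% | -7.1 | -9.0 | -9.4 |

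Wald passes all three and MN fails all three. Together they carry 30.1% of trials. One rarer table (3 v 4) brings the total Wald v MN disagreement to 30.3%. Wald is the one that passes each time.

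**3. Error and power, unstratified, no missing outcomes.** Every pair of binomial results was enumerated and the 8.5 rule applied. Error is taken at 90% v 98% (on the margin), power at 98% v 98%.

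| Limit | 54 per arm: error, power | 48 per arm: error, power |
|---|---|---|
| Wald | 4.4%, 77% | 6.3%, 80% |
| CC Wald | 2.9%, 72% | 2.9%, 61% |
| Newcombe | 1.6%, 46% | 1.7%, 47% |
| MN | 1.6%, 46% | 1.6%, 47% |

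No row meets 2.5% and 80% together. For MN at 54 per arm the error stays at or below 2.4% for control rates from 80% to 100%.

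**4. The disagreement depends on the pair.** At 54 per arm with no missing outcomes, Wald differs from MN or Newcombe in 30.3% of trials, but from CC Wald in only 4.2%. At 49 evaluable per arm (54 less about 10%, as in a PPS) the figures are 32.0% and 18.2%.

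**5. FAS, if WCCF counts missing as failure.** Success becomes 0.98 x (1 - missing) in both arms, at 54 per arm. Error is taken at a true 8-point difference in that FAS rate.

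| Missing | Wald error, power | CC Wald error, power | MN error, power | Wald v MN differ |
|---|---|---|---|---|
| 1% | 4.1%, 66% | 2.4%, 58% | 1.9%, 41% | 25% |
| 2% | 3.9%, 57% | 2.0%, 47% | 2.0%, 38% | 19% |
| 5% | 3.2%, 40% | 1.6%, 28% | 2.1%, 30% | 10% |
| 10% | 2.7%, 26% | 1.6%, 18% | 2.2%, 22% | 4% |

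**6. Centre weighting.** Simulation of a Wald limit with Mantel-Haenszel centre weights (four centres, balanced or one large) gave about 6.6% error and 84% power with unpooled within-centre variance, and about 5.0-5.4% and 79-80% with the Sato variance. Naming the weights alone would therefore not settle the matter; the variance matters too.

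**The case against.** **The method may be named elsewhere.** The SOP or the prospectus may do so, and this stands: what can be shown is that the supplied text is silent.

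**Late changes are restricted.** Section 8.6 places all analysis after final lock, 8.8 says that in principle the main methods are not changed and that changes are recorded, and 9.3 calls for a blind review report before lock. These are real safeguards. But a method that has not been named can be added without changing one, and finalisation before lock does not ensure that the choice precedes sight of outcomes. A reader might infer that the choice was left open on purpose, or will be made after unblinding; nothing in the documents supports that.

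**The 30% is one pair under one condition.** This also stands. A reader might infer that method choice flips about a third of trials in general. It does so for Wald against score-type limits with no missing outcomes. The two Wald limits differ in about 4% at 54 per arm, and the Wald v MN figure falls to 10% and 4% in the FAS at 5% and 10% missing. Nearly half of the 30% comes from 1 v 1, where MN misses the margin by only 0.2 points.

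**MN is not compelled.** Agreed. In the FAS, CC Wald holds 2.5% from about 1% missing and has more power than MN at 1-2% missing. It does not hold 2.5% at the planned rates with nothing missing.

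**The interval may be meant to be centre-adjusted.** Section 8.1.2(3) mentions centre adjustment and the interval together, so this is a fair reading. The enumerated figures are unstratified, and a stratified MN power cannot be derived without weights that the documents do not give.

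**Conclusion.** The concern holds. The decisive limit is undefined in the supplied text, the one named test does not address the stated null, and none of the four unstratified limits examined delivers the stated 2.5% error and 80% power together at 54 per arm. Power close to 80% appears only with Wald-type limits whose error exceeds 2.5%: 4.4% unstratified, and about 5-6.6% when weighted by centre. Score-type limits hold the error at about 1.6% but have about 46% power.

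A reader might infer that the non-inferiority decision rests on the CMH p-value and is therefore invalid. It does not: 8.5 rests the decision on the confidence limit.

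These figures assume equal arms, the same success rate in every centre, equal missingness in both arms and, for the FAS figures, that WCCF means failure, which 8.9 leaves open. The missing rates are illustrative; the documents give only a 10% maximum loss. Exact power moves in steps: for MN it is about 46-48% from 46 to 55 per arm and 59% at 56, so the 46% belongs to the planned size and should not be extrapolated.

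**What to change.** - **8.1.2(3) and 8.5:** before any outcome is seen, name one limit that holds one-sided 2.5%, its variance, and whether it is stratified by centre and with what weights. One example is the MN 95% interval for pT - pC, lower limit against -8%, with the matching score test of H0: pT - pC <= -8% at one-sided 0.025, so that interval and test cannot disagree. Apply the same method to FAS and PPS.
- **8.1.2(3):** label the CMH p-value descriptive.
- **8.9:** state whether WCCF counts a missing 6-month outcome as a failure.
- **8.2.1 and 8.3:** restate the power for exactly the method named. For unstratified MN it is about 46% at 54 per arm with no missing outcomes, and about 30% in the FAS at 5% missing counted as failure. A stratified limit needs its own calculation.

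The change is wording plus programming in the SAS 9.4 already planned. The real cost is that the stated power becomes much less favourable. The fix does not itself require a new sample size: the sponsor can accept the restated power openly or decide to re-size.

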5.3. Test Scopes

The test scopes of completely degradable occluder system: The current product is applied in the treatment of ventricular septal defect in congenital cardiac diseases;

The occluder surgical intervention delivery devices are dedicated in the surgical intervention operation, and they are used in the delivery of various occluders manufactured by the company into the lesion location for release. It is applied in the occlusion treatment for the atrial septal defects, ventricular septal defects and patent ductus arteriosus.

6. Products Indications and Contraindications, and matters in need of attention.

Indications:

Completely degradable ventricular septal defect occluder is a type of percutaneous ventricular

septal defects closure devices through catheter, used in the ventricular septal defects with abnormality of hemodynamics or enlargement of left ventricular inner diameter.

Contraindications:

- 1). Patients with moderate to severe resistant type pulmonary arterial hypertension.
- 2). There exists thrombus in the cardiac cavity. There is hemorrhagic diseases, such as active ulceration.

Matters in need of Attentions:

- 1). The degradable occluder system and occluder surgical intervention delivery devices have already been sterilized before discharge.
- 2). The product is disposable product, forbidden for application after resterilization after opening.
- 3). If it is discovered of the opening, damages, leakage of packages or over the sterilization validity period, please do not use it.
- 4). The selection of occluder delivery sheath is crucial, such defects as unmatched between the sheath tube and the occluder, may result in the delivery and withdrawal difficulty, even result in the blood vessel injury.
- 5). The product is only limited to the application by the physician already receiving occlusion technique trainings.
- 6). It is necessary to prepare for the emergency conditions, and withdraw the thrombus devices that may severely influence the flowing property of blood.
- 7). For allergic patients with polyactic acid, and poly (p-dioxanone), they may have allergic reaction for the product.
- 8). The product is applicable for MRI.
- 9). In order to avoid the adverse outcome, please read the manual carefully before application, in particular, it must take heed of all precautions and matters in need of attention.

7. General Design

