7.1.5. Selection of subjects

7.1.5.1. Inclusion Criteria

- (1) The subjects and (or) their legal guardians should know the nature of the current research, and consent to participate in the current clinical trial according to all the clauses of the current research. They must sign the informed consent approved by the ethics commission, and agree to receive the post-operative treatment protocol, and finish the follow up and relevant inspection required by the follow up, according to the follow up requirements.
- (2) Aged between one year and 60 years old, with body weight higher than 10kg, male or not pregnant women;
- (3) Effective shunt mouth for VSD is between 3mm and 14mm;
- (4) The upper margin of VSD is no less than a distance of 3mm from the right coronary valve of aorta, without aortic right coronary valve shedding into VSD and aortic regurgitation above moderate degree;

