13.1 Adverse Events

Definition of Adverse Events

Adverse events refer to adverse medical events that occur after the subjects accept the trial products, but they are not necessarily related to the trial products.

Selective operation, combined operation and other expected diseases that have been clearly

identified in the pre-enrollment diagnosis are not considered as adverse events.

Determination of severity of adverse events

Mild: Not influence on daily activities;

Medium: Influence on daily activities;

Serious: Loss of daily activities.

Determination of relationship between adverse events and devices

Affirmatively relevant;

Probably relevant;

Possibly relevant;

Possibly irrelevant;

Irrelevant.

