the occluder selected is too large, due to the small defect opening, the waist extension of the occluder is limited, and the edge is relatively long, or the disk of the occluder forms a spherical appearance, which occupies a larger space after release and affects tricuspid valve closure. Echocardiography monitoring shall be performed during the operation. If obvious tricuspid regurgitation is found, occlusion treatment shall be abandoned.

5) Aortic regurgitation

It is related to occluder and operation. For example, for VSD with poor edge, the edge of the occluder selected which is larger than the distance from VSD to aortic valve, and direct contact of the edge of the occluder with aortic valve will affect the closure of aortic valve.

The disc diameter of the left ventricle of the occluder is larger than 50% of the circumferential diameter of the outflow tract of the aortic valve, and after the occluder is placed, the outflow tract of the left ventricle can be deformed, resulting in incomplete closure of the aortic valve.

6) Residual shunt

Shunt through the occluder disappears in a short period of time after the polyester membrane mesh hole in the occluder is filled with blood components. Obvious residual shunt is found in patients treated by porous VSD occlusion because the occluder fails to completely cover the inlet and outlet. For porous VSD, the left of the occluder shall be ensured to completely cover the defect inlet, otherwise, the occlusion treatment shall be abandoned.

7) Hemolysis

It is related to the existence of residual shunt. High-speed blood flowing through the occluder can cause hemolysis, which is manifested as soy sauce urine, chills, anemia, renal insufficiency, etc. In this case, close observation shall be made. For patients with mild hemolysis, aspirin shall be stopped, hemostatic drugs shall be given intravenously, and sodium bicarbonate shall be given orally or intravenously. In case of shunt complicated with hemolysis caused by spring coil, another occluder or spring coil can also be placed. If hemoglobin < 70g/L, the occluder shall be removed surgically.

8) Acute myocardial infarction

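### The before/after safety count omits subjects already abnormal at baseline, so their worsening shows only if it is reported as an adverse event, and the plan leaves that unclear

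*Combined protocol and SAP*

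**What the plan says.** Section 8.1.2, item (4), sets out the safety analysis. It begins with a before/after count for each arm: "Describe the case number of normal before treatment and abnormal after treatment and their percentage". It does not name the tests to which this applies, and it has no category for a subject who was abnormal at baseline and became worse. The item then turns to adverse events: "Described the adverse events with the case number of adverse events and their occurrence", followed by "carried out continuous calibration χ^2 test or Fisher precision probability method test", and finally "it shall be described in details of the embodiment for all adverse events, their degrees and relevance with the research products". Section 8.9 bases safety evaluation on the Full Analysis Set.

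The flow chart in 7.2 schedules ECG and echocardiogram at screening and at six later points: during the operation, immediately after it, before discharge, and at 1, 3 and 6 months.

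On entry, inclusion criterion (4) in 7.1.5.1 asks for a defect "without aortic right coronary valve shedding into VSD and aortic regurgitation above moderate degree". Nothing in 7.1.5.1 or 7.1.5.2 names tricuspid regurgitation or conduction status on ECG.

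Section 13.1 defines an adverse event without requiring a normal baseline. It adds that expected diseases clearly identified at the pre-enrolment diagnosis do not count as adverse events, and 13.3 says the same for serious adverse events. Neither section mentions worsening of such a condition. The lowest step of the severity scale in 13.1 reads "Mild: Not influence on daily activities".

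**The concern.** A count of moves from normal to abnormal can register only subjects who start normal. Applied to a valve or a conduction finding, it gives no place to a subject whose mild regurgitation becomes severe, or whose bundle branch block becomes atrioventricular block.

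These are central risks for this device class. Section 13.4 forecasts arrhythmia (including bundle branch and atrioventricular block), tricuspid insufficiency and aortic regurgitation, and gives a mechanism for the last: "direct contact of the edge of the occluder with aortic valve will affect the closure of aortic valve". Section 4.1 offers avoidance of conduction block and valve damage as reasons for the degradable occluder. The ECGs and echocardiograms that would show worsening are already collected at every visit. If the readout drops part of that information, the two arms may look cleaner, and more alike, than the collected data would show.

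**Working it through.** **1. The denominator.** Section 8.2.1 gives 54 per arm, from 98% success in both arms, an 8-point margin, one-sided 0.025, 80% power and 10% dropout. With equal rates the protocol's formula becomes

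n = 2 × 0.98 × 0.02 × (1.960 + 0.842)² / 0.08² = 48.07, and 48.07 / 0.9 = 53.42, rounded up to 54.

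The figure reproduces. Nothing below changes it.

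**2. What the count can see.** For one parameter:

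| Baseline | After treatment | In the before/after count? |
|---|---|---|
| Normal | Abnormal | Yes |
| Abnormal | Unchanged or better | No |
| Abnormal | Worse | No |

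The third row is the gap. It follows from the wording of the rule and needs no assumption about rates.

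**3. Whether such subjects can be enrolled.** Aortic regurgitation: read literally, criterion (4) lets in anything up to moderate. If the translated phrase was meant to bar moderate as well, mild is still admitted. Tricuspid regurgitation and ECG conduction: no criterion names them. The documents do not say how many subjects will have these findings.

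**4. How many could fall in the gap (illustration only).** Let b be the share abnormal at baseline on a parameter and w the share of those who worsen. The documents give neither, so both are assumed ranges: b from 5% to 40%, w from 2% to 10%. The expected number of worsened subjects per arm outside the count is 54 × b × w. The chance of at least one, treating subjects as independent, is 1 − (1 − b × w)^54.

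| b | w = 2% | w = 5% | w = 10% |
|---|---|---|---|
| 5% | 0.05 (5%) | 0.14 (13%) | 0.27 (24%) |
| 10% | 0.11 (10%) | 0.27 (24%) | 0.54 (42%) |
| 20% | 0.22 (20%) | 0.54 (42%) | 1.08 (66%) |
| 40% | 0.43 (35%) | 1.08 (66%) | 2.16 (89%) |

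The ends of the range are 54 × 0.05 × 0.02 = 0.05 and 54 × 0.40 × 0.10 = 2.16 subjects per arm.

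**5. Whether another planned analysis picks them up.**

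- The adverse-event analysis in 8.1.2(4) does so if the investigator reports the worsening. The definition in 13.1 permits this. No text requires it for a change of ECG or echo grade, and the exclusion of conditions identified before enrolment can be read as removing it.
- The general rule in 8.1.2(1), frequencies and proportions for count data, gives totals. It does not pair a subject's baseline with the later result, so improvement in some can offset worsening in others.
- The echo classification in 7.1.6 concerns residual shunt and does not address valve function.

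**The case against.** The strongest reply is that adverse-event recording is the main safety method (7.1.7), that 13.2 requires every adverse event to be recorded, and that 8.1.2(4) counts, tests and describes them all. A reader might infer from the before/after sentence that worsening from an abnormal baseline is never counted. The documents do not support that, because the adverse-event route is open to it. Nor does the severity scale shut out silent events: its lowest grade is for events that leave daily activities unaffected. It may grade a silent rise in regurgitation low, but it does not exclude it. This part of the reply stands, and it limits the point to capture that is not assured.

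Three other strong readings also fail:

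- A reader might say that nobody can be normal before treatment on echo, since every subject has a septal defect. Section 8.1.2(4) names no parameter, and nothing says that echo is scored as one overall normal/abnormal item.
- A reader might apply the 3.8% pacemaker figure in 4.1 and conclude that such cases would go missing. The definition in 13.3 covers injury needing intervention and prolonged hospitalisation, and 13.4 discusses block and pacemakers under forecast serious events. These cases would be reported whatever the baseline ECG.
- A reader might note that coagulation is tested only at screening (7.2) and infer an empty cell in the table. The plan does not place coagulation in that table.

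Two further replies have some weight. Section 7.3.2 makes release of the occluder depend on ultrasound showing no effect on the aortic or tricuspid valve, which addresses acute worsening but not later worsening. Sections 8.7 and 8.8 refer to a statistical analysis prospectus, finalised before database lock, which could specify better tables. But 8.8 says the major methods would in principle not change, and grades that the eCRF did not capture may not be recoverable at that stage.

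**Conclusion.** The point holds as a gap in safety reporting. The before/after count cannot show worsening in a subject who was abnormal at baseline, the entry criteria admit such subjects for valve and conduction findings, and the only other route to the results depends on an adverse-event report that the plan does not clearly call for.

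The size is modest and uncertain: about 0.05 to 2.2 worsened subjects per arm outside the count, on assumed rates that the documents neither give nor contradict. At 54 per arm, one or two such subjects would matter to a safety comparison. The application to ECG and echo is itself a reading, since the sentence names no tests, and that baseline ECGs will include abnormal ones is an inference from the absence of any restriction. The primary test, the non-inferiority decision and the sample size are not affected.

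**What to change.** 1. In 8.1.2(4), for ECG conduction and for aortic and tricuspid regurgitation, replace the count with shift tables by arm: baseline grade against worst post-operative grade, from the visits already in 7.2. Report the number worsening by at least one grade at any visit and at 6 months, whatever the baseline.
2. Define the grades in advance. A workable set is none, bundle branch block, and first-, second- and third-degree atrioventricular block for ECG; and none or trace, mild, moderate and severe for each valve.
3. In 13.1 and 13.3, state that worsening of a condition present before enrolment counts as an adverse event, and as a serious one when it meets the serious criteria.
4. If the before/after count is kept for the laboratory tests, name the tests it covers.

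The cost is graded eCRF fields for ECG and valve regurgitation, one changed table, and a few more worsening events on display. No visit or test is added, and the sample size and primary analysis stay as they are.
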